Participants who meet the eligibility criteria and provide written consent to participate will be enrolled. This includes a pregnancy test for female volunteers that will be performed on the first day. Each participant will complete 3 different protocols of AIH delivery based on protocols derived from the literature that have been used to enhance motor function as well as a sham condition. Each delivery and testing session will last approximately 2 hours and be separated by at least 24 hours.

Inclusion criteria

Male and female participants between the ages of 18-40 years will be eligible to participate in the study unless they meet any of the following criteria.

Exclusion criteria

- a. Diagnosis of cardiovascular disease (Hypertension, arrhythmias, coronary artery disease, congenital and valvar heart diseases)
- b. Diagnosis of neuromuscular disease
- c. Diagnosis of any neurological disease
- d. Presence of concurrent medical illness including infection, fractures
- e. Diagnosis of obstructive sleep apnea
- f. Diagnosis of obstructive/restrictive lung disease
- g. Diagnosis of exercise induced asthma
- h. FEV1/FVC<80% and/or FVC<80% of predicted value indicating airway obstruction
- i. Subjects on prednisolone therapy or selective serotonin reuptake inhibitor (SSRI) therapy will be excluded from the study as these pharmacological agents are known to amplify the effects of IH[22, 23]
- j. Diagnosis of epilepsy or history of seizures and attention deficit disorders
- k. Pregnancy
- l. Diabetes
- m. History of coagulation disorders
- n. History of chronic pain
- o. Body mass index(BMI)> 35kg/m²
- p. Subjects on prescription medicines such as beta blockers and other drugs that are prescribed in any of the exclusionary disorders listed above.

Intervention

We will use a commercially-available hypoxicator that can be programmed to achieve a targeted level of arterial oxygen saturation. The fraction of inspired oxygen (FiO₂) during the hypoxic episodes will be adjusted to maintain pulse oximetry (SPO₂) between 80%-

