90%. In our experience, this can be achieved with a FiO₂ in the range of 9%-11 %. FiO₂ levels of 9% and 11% correspond to O₂ concentrations in room air at altitudes of 6500 meters and 5000 meters respectively, both altitudes humans are exposed to while on trekking expeditions and also have permanent human habitation [29, 30]. We will use alternating phases of hypoxia (FiO₂ :9%-11%) and normoxic or hyperoxic oxygen saturation with an FiO₂ between 22%-38%, based on the previous protocols used in human studies of motor function.

- A. 15 bouts of hypoxia for 1 minute, normoxia to hyperoxia 1 minute (Trumbower et al [12])
- B. 15 bouts of hypoxia for 2 minutes, normoxia to hyperoxia 1 minute (Hayes et al [13])
- C. 8 bouts of hypoxia for 2 minutes, normoxia to hyperoxia 1 minute (Tester et al [14])
- D. Sham hyperoxia (normoxia) for 2 minutes, normoxia to hyperoxia 1 minute

The order of the protocol will be randomly assigned for each participant who will remain blinded to the actual protocol they are receiving. All measures will be collected by a research assistant blinded to protocol assignment.

Outcomes

We propose to collect standardized measures of sensory function. Measures will be assessed at the hand and foot at baseline, immediately post- and every 10 minutes for 60 minutes after the AIH protocol.

Tactile:

Semmes-Weinstein filaments will be used to assess sensory thresholds. The patient will be in sitting position with shoes and socks removed. Starting with the weakest plastic kept perpendicular to the skin surface force will slowly be applied until there is a slight bend in the filament. The participant will indicate if they feel pressure. If not, the next filament is used and testing proceeds until the thinnest fiber that the participant can perceive is reached.

Pain sensitivity:

Participants will undergo quantitative sensory testing (QST) to determine pain sensitivity to thermal and pressure stimuli, as per protocols in our preliminary studies.

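### The stated participant and assessor blind is not protected: gas delivery lasts 24, 30 or 45 minutes by condition, the sham length is not given, and no masking of the timing is described

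*Combined protocol and SAP*

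**What the plan says.** The design is a crossover. Section 6 (Research Plan) states "Each participant will complete 3 different protocols of AIH delivery" as well as a sham condition, and "Each delivery and testing session will last approximately 2 hours and be separated by at least 24 hours". Under Intervention, the four conditions are:

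- A: "15 bouts of hypoxia for 1 minute, normoxia to hyperoxia 1 minute"
- B: "15 bouts of hypoxia for 2 minutes, normoxia to hyperoxia 1 minute"
- C: "8 bouts of hypoxia for 2 minutes, normoxia to hyperoxia 1 minute"
- D: "Sham hyperoxia (normoxia) for 2 minutes, normoxia to hyperoxia 1 minute", with no number of bouts

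Two sentences on blinding follow: "The order of the protocol will be randomly assigned for each participant who will remain blinded to the actual protocol they are receiving", and "All measures will be collected by a research assistant blinded to protocol assignment". Under Outcomes, the sensory measures are scheduled at baseline, straight after delivery, and then at ten-minute intervals for an hour. The Abstract (section 3) names sensory thresholds and tolerance as primary.

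The plan does not mention a common delivery length, where the assessor is during delivery, who operates the device, whether its displays are hidden, what participants are told about the conditions, or any check of the blind.

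**The concern.** Blinding is stated as a feature of the trial, but the delivery schedule, run as written, carries a timing signal that differs by condition. The assessor's baseline and immediate post-delivery readings bracket the delivery period, so its length can be seen from the testing timetable even by someone who never enters the room. Participants attend all four sessions and can compare them.

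The outcomes make this matter. Participants say when they feel a filament, end the heat stimulus themselves, and say when pressure becomes pain. Filaments and the dolorimeter are applied by hand. The cue arrives before the first post-delivery reading, so all seven post-delivery readings (one immediate, six at ten-minute intervals) come after it. The planned protocol-by-time analysis of covariance cannot separate an expectation effect from a protocol effect, because the cue changes whenever the protocol changes. A difference between hypoxia and sham, or between hypoxic protocols, would then be open to an explanation that the blind was meant to exclude.

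**Working it through.** **Inputs.** Bout counts and phase lengths for A to D come from section 6, Intervention. The plan states no delivery length per condition. Its only total is a session of about 2 hours, and the time needed for baseline testing and set-up is not given, so that total cannot be reproduced exactly.

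**Delivery length** = bouts × (hypoxia minutes + recovery minutes):

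- A: 15 × (1 + 1) = 30 min
- B: 15 × (2 + 1) = 45 min
- C: 8 × (2 + 1) = 24 min
- D: n × (2 + 1) = 3n min, n not stated

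The three hypoxic lengths are all different, with a spread of 45 − 24 = 21 min. If the last recovery minute is not delivered they become 29, 44 and 23 min, still all different.

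**Consistency with the stated session.** Delivery plus 60 min of post-testing gives 90 (A), 105 (B) and 84 (C) min. If a session is taken as 120 min, 30, 15 and 36 min remain for baseline and set-up. All three fit a session of about 2 hours, so that statement neither conflicts with the delivery lengths nor removes the difference between them.

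**Conditions with a unique length, for any sham length:**

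| Sham bouts n | Sham length | Same length as | Unique lengths |
|---|---|---|---|
| 8 | 24 min | C | A, B (2 of 4) |
| 10 | 30 min | A | B, C (2 of 4) |
| 15 | 45 min | B | A, C (2 of 4) |
| any other | 3n min | none | all (4 of 4) |

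The minimum is therefore two, and when there are exactly two, both are hypoxic. The pattern is the same without the last recovery minute. At n = 10 the sham and A share a total length but not a cycle: 3 min against 2 min.

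**What the cue is worth.** Assume an observer who knows all four lengths, uses only length, and labels one session of each kind.

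| | No cue | Sham matches one length | Sham matches none |
|---|---|---|---|
| Exact labels A to D, expected number right | 1 of 4 | 2 + 1 = 3 of 4 | 4 of 4 |
| Hypoxia or sham, expected number right | 1/4 × 4 + 3/4 × 2 = 2.5 of 4 | 1/2 × 4 + 1/2 × 2 = 3 of 4 | 4 of 4 |
| Chance of picking out the sham | 25% | 50% | 100% |

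The second and third rows bear on hypoxia-versus-sham contrasts, the first on contrasts between hypoxic protocols. These figures measure how informative the cue is. They do not measure bias.

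**The case against.** A reader might infer that the blind cannot hold, or that session length reveals assignments with certainty. The documents do not support that.

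- A length identifies a condition only to someone who can link lengths to conditions. Nothing says that participants are told the lengths, or that the assessor is present at delivery. That one assistant takes both the baseline and the post reading is a natural reading of the text, but it is not stated. Padding or separation of roles may exist and be undescribed.
- It is delivery that differs in length. The session is given as about 2 hours for every condition and could be made equal.
- If the sham has 8, 10 or 15 bouts, total length does not separate it from one hypoxic condition, and the gain in telling hypoxia from sham is modest (2.5 to 3 of 4).

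A reader might also suppose that any expectation effect would enter each contrast in full and in a known direction. Neither follows. The aim is to characterise the effect, with no stated direction; contrasts within a length-matched pair would not take the full shift; and there are partial safeguards, namely a heat stimulus that rises at a set rate and is ended by the participant, and a defined bend as the filament endpoint.

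These objections limit the claim but do not remove it. None supplies a sham length or a masking method. The assessor is also better placed than the participant to decode the timing, since study staff may reasonably be expected to know the four conditions.

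**Conclusion.** The concern stands in a limited form: the blind is not protected as written. At least two of the four conditions have a delivery length of their own, and whether it is two or four depends on the unstated number of sham bouts. The step from a visible cue to an identified condition assumes that someone knows or infers the condition lengths. That is plausible for the assessor and less certain for participants. Because the primary outcomes are subjective reports, a loosened blind could put expectation or tester bias into the protocol effect. The documents give no basis for the size or direction of that bias, so none is claimed. This should be corrected before a blinded comparison is reported.

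**What to change.** 1. State the number of sham bouts, and so the sham length.
2. Make mask time and the baseline-to-post interval the same in all four sessions. In the shorter conditions, add room-air time through the same running device after the baseline reading and before the first bout. The stated number and length of hypoxic bouts stay as they are.
3. Keep the assessing assistant away from delivery, and keep the oximeter and hypoxicator displays out of sight of participant and assessor. Say who runs delivery.
4. After each session, record the participant's and the assessor's guess of hypoxia or sham, and report the guesses beside any blinding claim. They are descriptive: a correct guess may reflect symptoms as well as timing.
5. Describe participant blinding as partial. Equal mask time does not hide 1-minute from 2-minute phases, or symptoms of hypoxia such as those listed in section 7.

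**Cost.** With B as the common length, mask time rises by 45 − 30 = 15 min in A, 45 − 24 = 21 min in C, and 45 − 3n min in the sham if it has at most 15 bouts. No session then becomes longer than B already is. Someone other than the assessor must run delivery. The stated assessor blind already implies this, but the plan does not describe staffing, so an extra person may be needed. The rest is protocol wording and two short entries per session.

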Protocol

1. Project Title

Effects of acute intermittent hypoxia on sensory function in healthy adults

2. Investigator(s):

[name]
[name]
[name]

3. Abstract:

Exposure to acute intermittent hypoxia (AIH) has safely induced facilitation of motor output in human studies. Despite this study, the affects of AIH on sensory function has not been established. We will use a commercially-available hypoxicicator that can be programmed to achieve a targeted level of arterial oxygen saturation. We plan to compare 3 previously published protocols that have generated motor facilitation (and a sham condition) to characterize and effects on sensory function in healthy adults. Primary outcomes will be measures of sensory function (thresholds and tolerance).

4. Background:

Brief intermittent episodes of hypoxia (or acute intermittent hypoxia [AIH]) induce plasticity in muscle motor neurons [1]. AIH activates carotid chemo afferents that stimulate episodic serotonin release [2, 3] which subsequently strengthens synaptic input and motor output of motor nuclei [3-8]. The persistent increase in phrenic nerve burst amplitude following repeated exposure to AIH is termed long-term facilitation (LTF) [9]. For example, increases in breathing capacity as demonstrated by a significant increase in minute volume has been demonstrated after exposure to AIH in unanesthetized and anesthetized rats [10, 11].

AIH has been demonstrated to be safe in healthy persons and has been routinely used in training athletes for many years. Similarly AIH is safe for people with neurological dysfunction (eg patients with chronic spinal cord injury (SCI)). In these patients, a single exposure to IH increased ankle plantar flexion torque by more than 80% [12]. Significant improvements in 10 meter walk times and 6 minute walk distances have been seen in patients with chronic SCI when IH was combined with walking at maximal sustainable exertion for 30 minutes [13].

Despite this promising work, the effect of AIH on sensory function has not been determined in humans, making this proposal a logical progression of the promising work done to date in improving motor function.

5. Specific Aims:

Our aim is to characterize how exposure to AIH protocols shown to enhance motor function impacts sensory function.

6. Research Plan:

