Study participants will undergo standard psychophysical pain testing using a contact thermode to deliver the evoked, thermal pain stimuli. The stimuli are to be applied by a research assistant who ensures proper thermode application and the range of stimulus intensities to be used (40-51°C) will be presented beforehand in ascending one-degree steps to each subject. We have found this procedure to be useful because it familiarizes subjects with the stimulus range, tends to obviate range effects in psychophysical scaling, and helps alleviate subject anxiety about the upper limit of stimulus intensities to be used. In order to standardize the scaling instructions and to clarify the distinction between the sensory intensity and affective dimensions of pain, a standardized instructional set will be used for all subjects. The research assistant will record numeric rating scale (NRS) response to each stimulus. The NRS will consist of a scale whose endpoints are

Protocol

Page 3 of 6

IRB version 03.09.04

PI version 3/18/2021 8:27 PM

designated as '0 - no pain sensation' and '100 - the most intense pain sensation imaginable'. In order to standardize the scaling instructions, standard instructions will be used for all participants.

Threshold and Tolerance. A continuous heat stimulus will be delivered to the subjects' dominant arm. The stimulus started at 35°C and will be increased at a rate of 0.5°C with subjects terminating the stimulus when the temperature reached pain threshold ("when the sensation first transitions from heat to pain") and tolerance ("when the sensation becomes so strong you want to remove it from your skin"). These procedures will be repeated three times and the average threshold and tolerance will be calculated.

Threshold and tolerance measures will also be collected using mechanical pressure applied using a Fischer Dolorimeter (Pain Diagnostics, Great Neck, NY). The tip of the dolorimeter is equipped with a rubber foot-plate of 1-cm diameter. During Dolorimeter testing, force is slowly increased until the subject indicates that the sensation changes from pressure to pain. Subjects are asked to rate any pain they are experiencing using a numeric rating scale (NRS) anchored at 0 (no pain sensation at all) and 100 (worst pain imaginable). Dolorimetry measures are made in the hand (1st dorsal interosseus muscle) and between the first and second toe on the dorsal aspect of the foot.

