Temporal summation. A train of 6 heat pulses will be applied to the glabrous skin of the foot. To ensure temporal summation, an inter-stimulus interval of 2 seconds will be used with temperatures starting at 39°C and increasing to 50°C (the TSA medoc maintains 10°C/sec rate in this range which is sufficient for maintaining the desired inter-stimulus interval). The participants will be asked to rate the magnitude of their delayed (second) pain sensation following each heat pulse. These response ratings are believed to be primarily C-fiber mediated.^{35,36}

We will test effects protocol using a two way (protocol and time) analysis of covariance with sensory measures as the dependent variables. Demographic variables that show an association with the sensory measures in our sample (eg gender differences have mixed evidence related to differences in sensory report) will be included as covariates.

7. Possible Discomforts and Risks:

Evoked pain: Risk of injury with this testing is minimal in that they are widely used and safe procedures. While pain is produced, risk to the individual is minimal, because 1) the pain is transient in nature and generally subsides immediately after the procedure; 2) subjects are instructed that they may stop any procedure at any time with no adverse consequences; 3) the level of pain experienced by subjects is below their tolerance level; 4) this pain will only last as long as the stimulus is applied (which is under the control of the study participant); 5) thermal stimulus intensity will not cause any damage to the study participant's skin. Some study participants will feel pain after the painful stimulus is removed, but no long-lasting pain perception (i.e. longer than 90s) is expected from quantitative sensory testing. Similarly a slight risk of burn is involved using thermal stimuli. The thermal stimulator

(Medoc TSA) has a built in shut off threshold that prevents the delivery of temperatures over 51 deg C. Our group has completed more than 1000 testing sessions in the past 5 years without any adverse events.

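### The only stated analysis of the primary outcomes, a two-way protocol-and-time ANCOVA, names no participant, session or repeated-measures term for 32 correlated readings per person, so as written its error rate is not controlled

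*Combined protocol and SAP*

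**What the plan says.** The Abstract (section 3) sets the primary outcomes: "Primary outcomes will be measures of sensory function (thresholds and tolerance".

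The design is in section 6, Research Plan. "Each participant will complete 3 different protocols of AIH delivery based on protocols derived from the literature", and each also completes a sham condition. On spacing: "Each delivery and testing session will last approximately 2 hours and be separated by at least 24 hours". Under Intervention: "The order of the protocol will be randomly assigned for each participant". Under Outcomes: "Measures will be assessed at the hand and foot at baseline, immediately post- and every 10 minutes for 60 minutes after the AIH protocol". For the heat stimulus: "These procedures will be repeated three times and the average threshold and tolerance will be calculated".

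The analysis is two sentences at the end of section 6. The first is "We will test effects protocol using a two way (protocol and time) analysis of covariance with sensory measures as the dependent variables". The second adds covariates: "Demographic variables that show an association with the sensory measures in our sample". No other passage describes an analysis. Neither sentence names a participant, session or period term, a repeated-measures or mixed model, a covariance structure, or a contrast of AIH with sham.

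**The concern.** The design is a four-period crossover with repeated readings inside each period. Readings from one person are alike, readings from one session are more alike, and neighbouring readings may be more alike still. A valid test compares each effect with the variation at its own level: protocol with session-to-session variation within a person, and protocol-by-time with variation within a session.

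A two-way analysis with only protocol and time pools all of this into one error. Demographic covariates cannot repair it. They vary only between people, so they remove at most part of the between-person variance and none of the session variance or serial correlation.

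This is the only stated test bearing on the study's single aim. If it is run as written, a significant protocol effect cannot be read at its nominal level, and a non-significant protocol-by-time effect carries little information.

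**Working it through.** **Inputs from the documents.** Four conditions (three AIH protocols and sham). Eight readings per session: baseline, immediately post, and 10, 20, 30, 40, 50 and 60 minutes. The three heat trials are averaged, so they add no readings. Hence 4 x 8 = 32 readings per participant for each measure and site.

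**Not in the documents, so assumed.** n = 20, two-sided alpha 5%, normal outcomes, and a range of variance shares (participant Vp, session Vs, residual Ve, summing to 1) and lag-1 correlations. There is no figure in the plan to reproduce. What follows is illustration only.

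**Formula.** In the two-way analysis, the protocol mean square reflects 8Vs + c·Ve, while the pooled error mean square is about Vp + Vs + Ve = 1. Here c = 1 + 2·Σ(1 − k/8)ρ^k for k = 1 to 7. That gives c = 1 for independent residuals, 3.08 for ρ = 0.6 and 3.83 for ρ = 0.7. The protocol F statistic is therefore multiplied by about R = 8Vs + c·Ve, and the type I error of the 3-df test is about P(χ²₃ > 7.815/R).

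Example: shares 0.6/0.2/0.2 with independent residuals give R = 8 x 0.2 + 0.2 = 1.8, and P(χ²₃ > 7.815/1.8 = 4.34) = 23%.

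| Vp/Vs/Ve | ρ | R | Formula | Simulated (4,000 null runs) |
|---|---|---|---|---|
| 0.8/0/0.2 | 0 | 0.20 | 0% | 0% |
| 0.7/0.1/0.2 | 0 | 1.00 | 5% | 7% |
| 0.3/0.1/0.6 | 0 | 1.40 | 13% | 13% |
| 0.6/0.2/0.2 | 0 | 1.80 | 23% | 24% |
| 0.4/0.2/0.4 | 0 | 2.00 | 27% | 27% |
| 0.7/0/0.3 | 0.6 | 0.92 | 4% | 5% |
| 0.6/0.1/0.3 | 0.6 | 1.72 | 21% | 22% |
| 0.3/0.1/0.6 | 0.6 | 2.65 | 40% | 41% |
| 0.2/0/0.8 | 0.7 | 3.07 | 47% | 48% |

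**Session drift.** In three further settings with a session-specific linear drift (20%, 30% or 50% of total variance), the protocol test rejected 6-8% of the time.

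**Protocol-by-time as written.** Its numerator contains only within-session variation, but it is divided by the full pooled error. It rejected about 0% of the time in all nine settings above, and 0.2%, 2% and 10% with drift shares of 0.2, 0.3 and 0.5.

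**With the error terms named.** In the same 12 settings, testing protocol against participant-by-protocol variation, with own-session baseline and period in the model, gave 4.5-5.7%. Protocol-by-time with a sphericity correction gave 4.0-5.8%; without the correction it gave 8-9% under serial correlation and 11-13% under drift.

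**Baseline adjustment alone is not enough.** With baseline as covariate but the seven post readings treated as independent, a contrast of the three AIH protocols with sham had a type I error of 21-30% across n = 10, 20 and 40.

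**Degrees of freedom.** As written, 32n − 32 = 608 at n = 20. Corrected protocol test: 4n sessions less n participants, 3 period, 3 protocol and 1 baseline terms, which is 3n − 7 = 53.

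**The case against.** The strongest reply is that both named factors vary within each person, so the phrase may be shorthand for a two-way repeated-measures analysis. The sentence is loosely drafted, and close parsing is weak evidence of intent. This stands as far as it goes: a reader might infer that the investigators mean to ignore the repeated measurements, and the documents do not show that. But they do not show the reverse either. Even the generous reading leaves open the error term for protocol, the use of baseline and the handling of serial correlation, and the figures above show that these choices matter.

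Three other strong inferences are not supported.

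- **That false positives are inflated.** With large between-person variance and stable sessions, the protocol test almost never rejects. The documents give no variances, so the direction is unknown.
- **That a planned AIH-versus-sham contrast has an error rate above 40%.** The text names no such contrast. That figure belongs to the overall four-condition test, and among the listed settings it arises only with a participant share of 0.2-0.3 together with lag-1 correlation of 0.6-0.7.
- **That a short-lived effect will be missed by some known margin.** That would need an effect size, variances and a sample size, none of which the documents give, and a comparison of the same test under both analyses.

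All the simulated outcomes are normal. Monofilament thresholds move in discrete steps, so the percentages do not carry over to that measure directly.

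**Conclusion.** The concern holds in this form: the only stated analysis of the primary outcomes omits any within-participant structure for 32 correlated readings per measure and site, and if followed as written it uses the wrong error for both protocol and protocol-by-time. That conclusion follows from the design and needs no particular variance value.

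Its size does depend on assumed values. At n = 20, type I error of the overall protocol test ranges from about 0% to 48% against a nominal 5%. Protocol-by-time rejects about 0% of the time without drift and up to 10% with strong drift. Separate runs at n = 10 and n = 40 gave a similar range for the protocol test. The analysis sentence should be corrected before any data are analysed.

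**What to change.** Replace the first analysis sentence at the end of section 6 with:

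> Each measure at each site will be analysed within participants by repeated-measures ANCOVA of the 7 post-exposure readings, with the session's own baseline as covariate and protocol, time, protocol-by-time and period as fixed effects, plus demographic covariates. Protocol will be tested against participant-by-protocol variation, and protocol-by-time against within-session variation with a Greenhouse-Geisser correction. If a mixed model is used instead, it will have a participant random effect and either a participant-by-session random intercept with a serially correlated residual or an unstructured within-session covariance, not both. The AIH-minus-sham contrasts (A, B and C against D), averaged over the 7 post readings, will be the main comparisons, with Holm adjustment across the three; contrasts at individual readings will be descriptive.

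The essential part is the error terms and the handling of serial correlation; baseline and period use information already collected.

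Notes on the choices:

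- An unstructured within-session covariance already absorbs a session intercept, so the two cannot be estimated together.
- A first-order autoregressive residual held its level in simulation without drift (protocol 3.6-5.9%, protocol-by-time 4.9-6.0%). With drift shares of 0.3 and 0.5 it did not: protocol 1.2% and 0.1%, protocol-by-time 7.7% and 10.2%. The unstructured option was not simulated.
- The plan should say how the Greenhouse-Geisser epsilon is estimated. In four settings, pooling it across protocols gave 3.9-4.7%, while the full interaction covariance gave a conservative 1.0-2.7%.
- Single-reading contrasts are kept descriptive because 3 x 7 = 21 unadjusted tests gave at least one false positive in about 47-61% of null simulations.

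Cost: a change of wording, fewer error degrees of freedom (53 instead of 608 for the protocol test at an assumed n = 20), and slightly less power from the Holm adjustment. No new readings, sessions or participants are needed.

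### The plan gives each session's pre-exposure reading no stated role; using it as a covariate for the post-exposure readings may sharpen the AIH-versus-sham contrasts

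*Combined protocol and SAP*

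**What the plan says.** The design is a four-session crossover. Section 6 states "Each participant will complete 3 different protocols of AIH delivery" and adds a sham condition. Sessions are spaced in time: "Each delivery and testing session will last approximately 2 hours and be separated by at least 24 hours". Under Intervention, "The order of the protocol will be randomly assigned for each participant".

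Under Outcomes, "Measures will be assessed at the hand and foot at baseline, immediately post- and every 10 minutes for 60 minutes after the AIH protocol". That is eight readings per session for each measure and site: one before exposure and seven after (immediate, then 10, 20, 30, 40, 50 and 60 minutes).

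The analysis paragraph that closes section 6 has two sentences. The first is "We will test effects protocol using a two way (protocol and time) analysis of covariance with sensory measures as the dependent variables". The second admits as covariates "Demographic variables that show an association with the sensory measures in our sample". Neither says whether the pre-exposure reading is a level of time, a covariate or something to be subtracted. Neither mentions a participant, session or period term.

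**The concern.** A person's sensitivity can differ from one day to the next. The reading taken just before exposure measures that day's starting point, and it is already collected in every session. On the most literal reading, with baseline as one level of the time factor, two things are lost. The protocol main effect averages in a reading taken before anything was given, and the day's starting level is not adjusted for.

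The demographic covariates cannot replace it. They are constant within a person, so with complete data and a participant term they cannot sharpen a within-person contrast. What is at stake is the precision with which each AIH protocol is compared with sham.

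**Working it through.** **Inputs from the documents.** Four conditions per participant; 1 + 7 = 8 readings per session. No sample size, effect, variance, correlation or significance level is given, so there is no planned figure to reproduce.

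**Assumed inputs.** n = 20; variance of a single reading 1, split into a stable person part, a session part v_s and a residual part v_r; constant effect 0.25 SD; session effect constant through the session; participant, period and protocol in the model; balanced periods; two-sided 5% per contrast.

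**Dilution.** With baseline as one of eight time levels, the main effect of a constant post-exposure shift d is (0 + 7d)/8 = 7d/8. For d = 0.25 this is 0.219.

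**Session-level variances.**
- Eight-level mean: v_s + v_r/8
- Post-only mean: v_s + v_r/7
- Baseline-adjusted: v_s + v_r/7 - v_s^2/(v_s + v_r)

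The SE of one protocol versus sham is sqrt(2v/n). Also rho_w = v_s / sqrt[(v_s + v_r/7)(v_s + v_r)], and adjusted SE / post-only SE = sqrt(1 - rho_w^2). At 0.2/0.2 the adjusted variance is 0.2286 - 0.04/0.4 = 0.1286, a fall of 44%; rho_w = 0.661 and the SE ratio is 0.75. Power is from the noncentral t with 54 df (53 adjusted).

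| v_s / v_r | rho_w | SE: 8-level / post-only / adjusted | Power: 8-level / post-only / adjusted |
|---|---|---|---|
| 0.2 / 0.2 | 0.66 | 0.150 / 0.151 / 0.113 | 30 / 37 / 58% |
| 0.1 / 0.2 | 0.51 | 0.112 / 0.113 / 0.098 | 48 / 58 / 71% |
| 0.05 / 0.2 | 0.36 | 0.087 / 0.089 / 0.083 | 70 / 79 / 84% |
| 0 / 0.2 | 0 | 0.050 / 0.053 / 0.053 | 99 / 100 / 100% |

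The step from the first to the second power figure comes from keeping baseline out of the average. The step from the second to the third comes from adjustment. Subtracting the baseline instead has variance 8v_r/7 = 0.2286 in all four rows, hence 37% power, and is never better than adjusting.

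**Unbalanced orders.** The plan says only that order is random. Simulating freely randomised orders with a period term (4,000 runs) gives 28/35/55% in the first row instead of 30/37/58%.

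**Drift within a session.** Exposure takes 15 x (1+1) = 30 minutes for protocol A, 15 x (2+1) = 45 for B and 8 x (2+1) = 24 for C. With B, the last reading therefore comes about 45 + 60 = 105 minutes after baseline. Suppose the correlation of the session effect decays exponentially, with a 45-minute gap before the first post-exposure reading. At 0.2/0.2:

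| Decay constant (assumed) | Variance: post-only to adjusted | Power: post-only to adjusted |
|---|---|---|
| none (constant) | 0.229 to 0.129 | 37 to 58% |
| 120 min | 0.195 to 0.166 | 42 to 48% |
| 60 min | 0.170 to 0.161 | 47 to 49% |
| 30 min | 0.136 to 0.135 | 56 to 56% |

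**Need for the participant term.** This was simulated with n = 20, person variance 1, and session plus residual variance 1. With no session variance and no participant term, adjusting for baseline raises the true SD of the contrast from 0.124 to 0.204, while the SE that the model reports falls from 0.349 to 0.259. With the participant term, the true SD goes from 0.124 to 0.126.

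**Fading effect.** Let the effect fall linearly from 0.5 SD to 0 over the seven readings (mean 0.25), equally in all three AIH protocols. The 21-df protocol-by-time test including baseline then has 71% power, against 57% for a 3-df baseline-adjusted protocol test, at 0.2/0.2. At 0.3/0.1 the figures are 98% and 75%. The 18-df protocol-by-time test on post-exposure readings alone has 60% and 94%. For a constant 0.25 the order reverses: 15% for the 21-df test against 57% at 0.2/0.2.

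**The case against.** The strongest reply is that the crossover has already done most of the work. Stable differences between people cancel in every AIH-versus-sham contrast, so baseline helps only through day-to-day variation within a person that lasts from before exposure to an hour after it. The documents give no evidence on the size or persistence of that variation. This stands: a reader might infer that adjustment would sharpen every contrast, but the gain runs from nil to large and nothing in the plan places the trial in that range.

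Second, seven readings over an hour and a time factor suggest that time course may be of interest. If the effect fades, the pre/post interaction is the more sensitive test. This also stands. The documents do not state the expected shape, so they do not support calling the averaged protocol effect the only proper primary term.

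Third, filament readings are discrete steps, and the thermal device cuts off above 51 deg C, which can cap heat tolerance. The power figures assume normal errors and need not carry over to those measures.

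None of this supplies a role for the baseline. For a sustained effect, no computed case showed a meaningful loss from adjusting once participant is in the model.

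**Conclusion.** The point holds as a conditional gain in precision. The plan names no use of the session baseline as a covariate. If baseline is one of eight time levels, the protocol main effect is 7/8 of a constant effect and is unadjusted for the day's starting level. Adjustment multiplies the post-only SE by sqrt(1 - rho_w^2). In the assumed cases with a constant session effect, that adds 21 percentage points of power at 0.2/0.2, 5 at 0.05/0.2 and none at 0/0.2. Drift within the session reduces the 21 points to 6, 2 or none.

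Two stronger readings are not supported. A reader might infer that the planned comparison is biased; it is not shown to be, since order is random and the 7/8 factor is a known dilution of a constant effect. A reader might also infer that the plan does treat baseline as a level of time, or omits participant from the model. The text is silent on both, and silence does not show which was intended. This is worth considering, not a defect that undermines the trial.

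**What to change.** State that, for each measure and site, the seven post-exposure readings are analysed in a mixed model with participant, random session within participant, period, protocol, time and protocol-by-time. Use that session's baseline for the same measure and site as covariate. If participant is random, add the participant's mean baseline, so that the slope on the session value is a within-person one. Session must be random: each participant has one session per protocol, so a fixed session term would absorb both protocol and baseline.

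Report each AIH protocol versus sham averaged over the post-exposure readings, and report protocol-by-time for waning. Which of these is primary is the investigators' choice, to be stated in advance. Choose a suitable scale or model for the filament readings and for heat tolerance capped by the device.

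The cost is analysis wording and one degree of freedom (two with participant random); no new data are needed. There is no gain if rho_w is near zero. The averaged contrast is less sensitive than the pre/post interaction if the effect fades, which the reported protocol-by-time test partly recovers.
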